Reducing Hemarthrosis in High Tibial Osteotomy and Tibial Tubercl Osteotomy by the Administration of Intravenous Tranexamic Acid: A Prospective, cohort study

Regulatory Sponsor: *NYU Langone Health
Langone Orthopedic Hospital
[name]
New York, NY 10003*

Principal Investigator: *[name]
Division of Sports Medicine
New York University Hospital for Joint Diseases
New York, NY 10003
Office: [contact]*

Protocol Number: **18-00535**

Version Date: **June 4, 2018**

NCT03606109

I. PURPOSE OF THE STUDY AND BACKGROUND

Purpose

The purpose of the proposed study is to evaluate the effects of administering intravenous tranexamic acid (TXA) to patients undergoing high tibial osteotomy (HTO) and tibial tubercle osteotomy (TTO) to minimize hemarthrosis within the knee joint and post operative pain and swelling.

Rationale

High tibial osteotomy is a procedure performed to correct varus malalignment and slow the progression of medial osteoarthritis or correct knee instability caused by varus malalignment¹. Tibial tubercle osteotomy is a procedure performed to treat patellar instability or overload of the patella². The tibial tubercle is a bony prominence where the patella attaches found on the anterior tibia, inferior to the knee joint. Both patients requiring HTO and TTOs suffer from chronic knee pain. During the process of an osteotomy, extensive bone bleeding can occur due to the opening gap³. As a result, complications of both procedures include postoperative bleeding and swelling of the knee joint, which prolongs healing and the rehabilitation process.

Tranexamic acid (TXA) has been proposed as a solution to decrease these postoperative complications. TXA is a synthetic anti-fibrinolytic agent that competitively inhibits the activation of plasminogen to plasmin by blocking tissue plasminogen activator and at higher concentrations directly inhibits plasmin^{4,5}. Plasmin, an enzyme that degrades fibrin clots, fibrinogen, procoagulant factors V and VIII⁴. Inhibition of plasmin decreases proteolytic action thus leading to clot formation and stabilization⁴. TXA is indicated in patients with hemophilia for short-term use (two to eight days) to reduce or prevent hemorrhage and reduce the need for replacement therapy during and following tooth extraction⁶. Administering TXA during the surgery will reduce the amount of plasmin in the system decreasing blood loss during and after the surgery. One gram of intravenous tranexamic acid (TXA) will be administrated before tourniquet inflation and before closure of the incision, as 1 g has been shown to be a safe amount with minimal side effects⁷. TXA has already been shown to decrease perioperative bleeding in total knee arthroplasty and total hip arthroplasty, without increasing the risk of deep vein thrombosis⁸⁻¹⁴.

This study is not being conducted under an IND number and will be conducted under IND exemption. This investigation is not intended to be reported to the FDA in support of a new indication for use nor support any other significant change in the labeling or advertising for the drug. The investigation does not involve a route of administration or dosage level or use in a patient population or other factor that significantly increases the risks (or decreases the acceptability of the risks) associated with the use of the drug product. The route of administration (IV) and dosage of 1 g has been shown to be safe and effective^{6,7}. The investigation is conducted in compliance with the requirements for institutional review set forth in part 56 and with the requirements for informed consent set forth in part 50; and The investigation is conducted in compliance with the requirements of 312.7.

We hypothesize that administration of TXA will reduce perioperative bleeding in osteotomy procedure with minimal side effects. As a result, swelling and postoperative pain will decrease thus improving postoperative outcomes. While TXA has been used in various orthopedic surgeries to reduce bleeding, no study has investigated the efficacy of TXA during a TTO procedure and TXA during HTOs have limited available studies. The available literature shows perioperative bleeding and hematoma significantly decreased during HTO procedures³. By comparing high tibial osteotomy patients to tibial tubercle osteotomy patients, we will determine if there is a difference in efficacy or if both cohorts will be similarly affected.

Study Design

This is a single-center, prospective cohort study. Patients will be assigned to their cohorts based on diagnosis and appropriate treatment as determined by the surgeon. Patients will be consented in the study once they are scheduled for either a HTO or TTO, therefore this will not be a randomized study. The study is comparing blood loss and postoperative pain after TXA administration in patients receiving a high tibial osteotomy (HTO) to patients receiving a tibial tubercle osteotomy (TTO) with or without medial patello-femoral ligament (MPFL) reconstruction. One gram of intravenous tranexamic acid will be administered before tourniquet inflation and 1 gram of IV TXA before closure of the incision. Patients will be asked on postoperative day 1, 2 and 7 to rate their pain according to the VAS scale. Patients will have their knee swelling measured immediately postoperatively and at their one-week follow up visit. The swelling ratio is defined as the postoperative mean circumference of upper pole of patella and lower pole of patella divided by the preoperative values.

Primary Objective

The primary objective of the study is to determine if there are any differences in blood loss between patients undergoing high tibial osteotomy (HTO) and tibial tubercle osteotomy (TTO) with or without medial patello-femoral ligament (MPFL) reconstruction.

Secondary Objective

Secondary objective of the study is to determine if there is a difference in post operative pain and swelling between patients undergoing HTO compared to patients undergoing TTO.

II. CHARACTERISTICS OF THE RESEARCH POPULATION

Number of Subjects

The total number of subjects enrolled will be approximately forty (40) patients, with 20 patients in the HTO cohort and 20 patients in the TTO cohort, calculated by post hoc analysis. The Patients will be recruited from routine clinical practice at The NYU Langone Health, Langone Orthopedic Hospital, Sports Medicine Division.

Gender of Subjects

Men and women will be included in this study.

Age of Subjects

Subjects included study will be at least 18 years of age.

Racial and Ethnic Origin

There are no enrollment restrictions based on race or ethnic origin.

Inclusion Criteria

Patients will be screened for eligibility using the following criteria. All study subjects must meet the following inclusion criteria:

- Patients undergoing a high tibial osteotomy (HTO)
- Patients undergoing tibial tubercle osteotomy (TTO) with or without medial patello-femoral ligament (MPFL) reconstruction
- Patients ages 18-60, inclusive

Exclusion Criteria

Patients meeting the following criteria will be excluded from participation in this study:

- Legally incompetent or mentally impaired (e.g., minors, Alzheimer's subjects, dementia, etc.)
- Younger than 18 years of age
- Older than 60 years of age
- Any patient considered a vulnerable subject including: pregnant women or fetuses, children, cognitively impaired adults, prisoners
- history of coagulation abnormalities and thromboembolic disease or current abnormal coagulation test values
- history of stroke or acute coronary syndromes within 3 months before surgery
- Preoperative (chronic) anticoagulation therapy
- Abnormal coagulation profile
- Renal failure (serum creatinine $> 250 \mu\text{mol/L}$ [2.83 mg/dL]) or liver cirrhosis
- Sickle cell disease
- Patients with a history of hypersensitivity to Percocet and/or TXA

Vulnerable Subjects

We do not intend to enroll vulnerable subjects.

Subject withdrawal criteria. Patients are free to withdraw at any time from the study.

III. METHODS AND PROCEDURES

Methods and Procedures

Patients indicated and scheduled for a high tibial osteotomy or tibial tubercle osteotomy with or without medial patello-femoral ligament reconstruction will be identified from faculty surgeon case logs at the NYU Langone Health, Langone Orthopedic Hospital Sports Medicine Division. After informed consent is obtained, a chart review of patients' medications and past medical histories will be reviewed based on their electronic medical records to identify any current pain medications or exclusion criteria. Patients will be in the study for 1 week, until their first follow up visit.

Patients will be given 1 gram of intravenous tranexamic acid (TXA) before tourniquet inflation and 1 gram of IV TXA before closure of the incision. Immediate post-operative management will not be affected by this study. The study team will not be blinded to the study as there is no randomization to each cohort. All patients will receive a standardized regimen of aspirin for DVT prophylaxis and Percocet for pain management, which is standard of care post-operative treatment.

Information to be recorded pre-operatively includes age, sex, height, weight, BMI, and American Society of Anesthesiology (ASA) classification. Intra-operative information will also be recorded, including operative time, and estimated blood loss. During the surgery, a suction device is utilized to remove excess blood from the surgical site and sucked into the suction drain and placed into a measuring cup. We will measure the perioperative blood loss by look at the measuring cup and seeing how much blood is inside. Knee swelling postoperatively will be measured using the swelling ratio. The swelling ratio was defined as the circumference of the operative limb divided by the circumference of the contralateral limb. Pain severity scores at rest will be assessed by use of a visual analog scale (VAS; 0 = no pain, 10 = worst pain imaginable) at 0.5, 1, 1.5, 2, 4, 6, 24, and 48 hours as well as 7 days after surgery. Percocet consumption will be recorded at 24 hours, 1 day, 2 days and 7 days after surgery. Incidence of TXA-related side effects (nausea/vomiting, itching, anxiety, increased thirst, rapid heartbeat) in the first 24 hours will be noted. Time to discharge from the post-anesthesia care unit (PACU) and time to discharge from the hospital will be recorded.

Analysis and Data Monitoring

Data monitoring will be done by [name], the principal investigator. He will review the following accumulated data quarterly.

He will monitor whether or not:

1. Collection and storage of patient data was performed in a sensitive and secure manner, as defined in the informed consent form and protocol, ensuring information is stored on REDCap.
2. All study activities were conducted with primary emphasis on patient care and wellbeing, ensuring the patients are not in discomfort and have an abnormally high VAS following the surgery.
3. If there were any adverse events, and if so were addressed appropriately and per protocol
4. The risk/benefit to patients has remained the same throughout the course of the study.

The study will be stopped if there are unexpected severe AE's in more than one patient. Adverse events will be defined as negative reactions to the intravenous TXA during or after surgery, including seizures, vision problems. We will submit summaries of data and safety monitoring annually.

Data Analysis

According to a post hoc power analysis calculating the effect size using our preliminary data, >15 patients are required with $d=0.6$ to obtain a power of 0.80 and an alpha value of 0.05. Therefore we are including an additional 5 patients per group to account for patients that may be

lost to follow up. Statistical analysis will be performed using chi-squared and/or fisher's exact testing depending on size for binary variables. Continuous variables will be compared with paired t-tests if the data is approximately normally distributed. If the data is not normally distributed, Mann-Whitney tests will be used. All protected health information will be removed prior to statistical analysis. We will use patient subjective pain, perioperative blood loss and knee swelling data as statistical endpoints. Subjective pain will be measured with the VAS (visual analogue scale), perioperative blood loss will be measured looking at blood loss from the suction drain after surgery. The swelling ratio is defined as the postoperative mean circumference of upper pole of patella and lower pole of patella divided by the preoperative values according to our previous study. The endpoints must be statistically significant between the two cohorts to show TXA is effective.

Data Storage and Confidentiality

Data recorded from this study will be organized in RedCap and maintained on the department's secure password-protected research drive until the data are de-identified. Participant medical information will only be available to the principal investigator and research staff as necessary for data analysis. All patient health information will be de-identified and assigned a code. Information linking participants' names, social security numbers and medical record numbers will be stored in a secure location separate from the medical information. This information will be destroyed at study closure.

Adverse Event Reporting

Information about any breach of confidentiality will be documented in the electronic data collection system and/or on the paper CRFs, as appropriate. It will be the responsibility of the Principal Investigator to report any Serious Adverse Event (SAE) that occurs during the data collection to the Institutional Review Board (IRB) within the timeframe specified by NYU SoM.

IV. RISK/BENEFIT ASSESSMENT

Risk

This study involves risk of medication side effects as well as a breech of confidentiality.

Intravenous TXA can cause the following side effects:

- Anxiety
- blurred vision
- changes in vision
- chest pain
- confusion
- cough
- dizziness or lightheadedness
- fainting
- fast heartbeat
- greatly increased or decreased frequency of urination or amount of urine
- increased thirst
- loss of appetite
- nausea or vomiting

- numbness of the hands
- pain, redness, or swelling in the arm or leg
- sudden shortness of breath or troubled breathing

Rare side effects include:

- Convulsions or seizures
- Orthostatic hypotension
- sweating
- trouble seeing
- unusual tiredness or weakness.

Protection against Risks

The patients will stay in the recovery unit a minimum of 3 hours after surgery as the mean duration of the effect of TXA is 3 hours and be monitored by the recovery unit nurses^{15,16}. Patients will be instructed to call the principal investigator and visit the emergency department if there are any symptoms of calf swelling or chest pain within the first seven days following surgery.

All patients will be de-identified and given a code. Information linking the patient codes to the participants' names and medical record numbers will be stored in a secure location separate from the medical information. Access to the information linking the linkage codes with participant identifiers shall be restricted.

Potential Benefits to the Subjects

Patients may experience less pain post-operatively, and may require less narcotics use, which has a steeper side-effect profile. However, these benefits cannot be guaranteed.

Additionally, it is the hope of the research team that results of this study will benefit future patients and their physicians by providing more information regarding the efficacy of TXA during surgery. This will allow for a more open and informed dialogue, and possibly a change in standard of care.

V. INVESTIGATOR'S QUALIFICATIONS AND EXPERIENCE

The CV, medical license, and human subjects' tutorial completion report are attached for all investigators who are participating in this study. All research personnel have medical research experience and are qualified to participate in this quality study. Most importantly, staff have been properly educated and certified with CITI training to conduct research in a matter that will maintain full patient confidentiality. The research coordinator for this study is trained in GCP principles and practices and will be responsible for compliance with GCP guidelines for all study investigators and research assistants.

VI. SUBJECT IDENTIFICATION, RECRUITMENT AND CONSENT/ASSENT

Method of Subject Identification and Recruitment

Case logs of participating faculty in the NYU Langone Health, Langone Orthopedic Hospital, Sports Medicine Division will be examined for patients that are scheduled for HTO or TTO with or without MPFL reconstruction. All potential subjects will be patients of the faculty in the NYU Langone Health, Langone Orthopedic Hospital, Sports Medicine Division.

Process of Consent

Written consent will be obtained from subjects who are eligible candidates for HTOs and TTOs based upon their medical condition (as determined by their physician). The consent process will take place during the office visit when it is determined necessary to perform the procedure—at which time the investigator has determined subject's voluntary participation has been upheld. Subjects will be informed about the study and the intended purpose. They will be given the opportunity to ask questions and receive thorough explanations. They will be made aware of the possible risks and anticipated benefits. They will also be informed of alternative procedures. Subjects will then be given another opportunity to ask questions and agree or disagree to consent.

Subject Capacity

All subjects enrolled in this study will have capacity to provide informed consent.

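### The plan offers similarity of the two cohorts as one of only two conclusions, but gives no margin or interval that could support it with 20 patients per group

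*Combined protocol and SAP*

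**What the plan says.** Section I, Rationale, describes what the HTO-TTO comparison will deliver: "we will determine if there is a difference in efficacy or if both cohorts will be similarly affected". These are the only two outcomes named; an inconclusive result is not among them.

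Section III, Data Analysis, lists the methods: chi-squared or Fisher's exact tests for binary variables and, for continuous variables, "Continuous variables will be compared with paired t-tests if the data is approximately normally distributed", with Mann-Whitney tests otherwise. All of these test for a difference. Neither this section nor any other gives an equivalence margin, an equivalence test or a confidence interval.

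The same section contains the plan's one written decision rule: "The endpoints must be statistically significant between the two cohorts to show TXA is effective".

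On size, Section II, Number of Subjects, plans "approximately forty (40) patients, with 20 patients in the HTO cohort and 20 patients in the TTO cohort". Data Analysis states that ">15 patients are required with $d=0.6$ to obtain a power of 0.80 and an alpha value of 0.05" and adds 5 per group for loss to follow-up. The effect size is attributed to preliminary data; the endpoint and contrast it describes are not given.

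**The concern.** A test of no difference can reject the null hypothesis or fail to reject it. Failing to reject is not evidence that two groups are alike, least of all in a small study. To conclude similarity, a plan needs a criterion, usually an interval lying wholly inside a margin fixed in advance. This plan names the conclusion and gives no criterion, so a non-significant p-value is all an analyst would have to reach it with.

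The plan also points two ways on the same null result. The Rationale leaves it to be described as similarity of effect. The rule in Data Analysis makes it a failure to show that TXA works. If neither reading is fixed beforehand, the choice can be made after the result is known. At stake is a published statement that the two procedures respond alike, resting on data that remain compatible with a difference as large as the one the plan itself names.

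**Working it through.** **Inputs**
- n = 20 per group (Number of Subjects).
- d = 0.6, alpha = 0.05, power = 0.80 (Data Analysis). Sidedness is not stated; two-sided is assumed.
- Loss allowance of 5 per group, leaving 20 − 5 = 15 (Data Analysis).
- Test: the plan names a paired t-test, but the cohorts are different patients, so a two-sample t-test is used here. Results are in SD units because the documents give no SD.

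**1. The plan's own figure.** For two independent groups, normal approximation:

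n per group = 2 × (1.960 + 0.842)² / 0.6² = 43.6, so 44 (45 with the t distribution).

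A one-sided test needs 35 (36 with t). A paired t-test needs 24 pairs two-sided or 19 one-sided. The closest variant, paired and one-sided by normal approximation, gives 18. None gives the stated figure of just over 15, so d = 0.6 serves below as the plan's only stated benchmark, not as a difference the study is powered to detect.

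**2. Precision at n = 20.** Half-width = t(2n − 2) × √(2/n).
- 95% interval: 2.024 × √(2/20) = 2.024 × 0.3162 = 0.640 SD.
- 90% interval: 1.686 × 0.3162 = 0.533 SD.

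Since 0.640 > 0.6, an observed difference of exactly zero gives a 95% interval of −0.64 to +0.64 SD, which contains both −0.6 and +0.6.

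**3. How often a real difference would be non-significant.** With true d = 0.6 and n = 20, the non-centrality is 0.6 × √(20/2) = 1.897, the critical value is 2.024 and the power is 0.456. The chance of non-significance is 1 − 0.456 = 0.544, about 54%.

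**4. How often similarity could be shown if it were true.** Taking ±0.6 SD as an assumed margin (the documents give none) and a true difference of zero, both limits are excluded at n = 20 in about 4% of studies with a 95% interval and 18% with a 90% interval.

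**5. If only 15 per group remain.** The 95% half-width is 2.048 × √(2/15) = 0.748 SD. Power at d = 0.6 is 0.355, so non-significance occurs about 65% of the time. This case applies mainly to the day-7 outcomes. Blood loss is read from the suction container at surgery and should not be lost with follow-up.

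**6. The two readings of a non-significant result**

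| Section | Reading available |
|---|---|
| I, Rationale | the cohorts are affected alike |
| III, Data Analysis | TXA is not shown to be effective |

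These are different conclusions from one result. Because every patient receives TXA, the HTO-TTO contrast has no untreated comparator and supports neither.

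**The case against.** The strongest reply is that the plan never says it will treat non-significance as similarity. The sentence is one line of Rationale. The primary and secondary objectives ask only whether outcomes differ, and a study looking for a difference needs no equivalence margin. The written rule in Data Analysis reads a null result another way. This stands as far as it goes: a reader might infer that every non-significant result will be declared similar, and the documents do not support that. What remains is that similarity is offered as a determination, with no criterion for it and a competing rule elsewhere.

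Three further readings also go too far:
- **That 20 per group can never exclude 0.6 SD.** A 90% interval, as used with two one-sided tests, could just do so if the observed difference were below about 0.6 − 0.533 = 0.067 SD. A 95% interval can also exclude one direction without the other.
- **That the 15-per-group figures describe the primary endpoint.** The allowance is for loss to follow-up, which should not remove blood loss measured at surgery.
- **That an agreed margin in mL would rescue the claim.** The documents give no SD or mL value on which to base one. Similar blood loss in two cohorts that both received TXA would still not show that TXA affected them alike.

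It can also be said that the 54% figure measures low power, which is a separate matter. That is fair. It is used here only to show how often the similarity wording would be within reach when a difference of 0.6 SD exists.

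**Conclusion.** The point holds in a limited form. The plan offers a similarity conclusion that its methods cannot support, and two of its sections imply different readings of a non-significant result. At 20 per group the 95% interval extends 0.64 SD either side of the estimate, against the plan's only effect size of 0.6 SD, and a true difference of that size would be missed about 54% of the time.

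These figures assume a two-sided two-sample t-test at 0.05, roughly normal data with a common SD, and all 20 patients per group evaluable. They treat d = 0.6 as a benchmark whose endpoint is unknown. The absence of any similarity criterion depends on none of these assumptions. The change is worth making because it alters what the study may conclude.

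**What to change.** 1. In the Rationale, delete the second alternative in the sentence, everything after the word efficacy, and recast the rest as a comparison of outcomes between the two procedures.
2. In Data Analysis, report the HTO-TTO difference in blood loss, and in pain and swelling, each with a 95% confidence interval.
3. State there that a non-significant result is inconclusive: it shows neither similarity between the cohorts nor anything about TXA efficacy, because all patients receive TXA.
4. Reconcile the decision rule in Data Analysis with this statement, so that a null result has one reading throughout.

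The cost is wording and a routine addition to the analysis output; no extra patients or procedures are needed. The downside is that the study will probably have to report an inconclusive comparison where it might have reported a similar one.

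### The HTO–TTO comparison cannot show that TXA works, because every patient receives it, and the paired t-test does not fit two unmatched cohorts; covariate adjustment is an optional extra

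*Combined protocol and SAP*

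**What the plan says.** **Cohorts.** Study Design: "Patients will be assigned to their cohorts based on diagnosis and appropriate treatment as determined by the surgeon". The study is not randomised and describes no matching. Under Methods and Procedures, every patient in both cohorts receives TXA.

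**Objectives.** The primary objective asks whether blood loss differs between HTO and TTO patients. The secondary objective asks the same of pain and swelling. Neither mentions TXA efficacy.

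**Interpretation.** Two other places go further. Rationale: "By comparing high tibial osteotomy patients to tibial tubercle osteotomy patients, we will determine if there is a difference in efficacy". Data Analysis: "The endpoints must be statistically significant between the two cohorts to show TXA is effective".

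**Tests.** Chi-squared or Fisher for binary variables. For the rest: "Continuous variables will be compared with paired t-tests if the data is approximately normally distributed", and "If the data is not normally distributed, Mann-Whitney tests will be used". No regression, stratification or matching is named, although age, sex, BMI and ASA class are recorded before surgery.

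**Pain and swelling.** Every listed VAS time is postoperative: nine times under Methods and Procedures, and in Study Design "Patients will be asked on postoperative day 1, 2 and 7 to rate their pain according to the VAS scale". Study Design and Data Analysis define the swelling ratio by "circumference of upper pole of patella and lower pole of patella divided by the preoperative values"; Methods and Procedures divides by the contralateral limb instead.

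**The concern.** Two statements in Data Analysis would mislead if followed. The efficacy sentence turns a comparison of two procedures into a verdict on a drug that both groups receive. The trial could declare TXA effective because one operation bleeds more than the other, or declare it ineffective because both bleed alike. The paired t-test presupposes pairs that the design does not create.

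A lesser matter is that the cohorts may differ in age, sex, BMI and prior pain. From the crude result alone, a reader cannot tell how much of a difference reflects measured patient mix. The means to show this are mostly already in the data.

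**Working it through.** **1. What the difference contains.** Let m_H and m_T be the mean outcomes without TXA, and e_H and e_T the reductions due to TXA. Then

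observed difference = (m_H − e_H) − (m_T − e_T) = (m_H − m_T) − (e_H − e_T).

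- If TXA works equally in both procedures, e_H − e_T = 0 and the difference is m_H − m_T, whether the effect is large or nil.
- If TXA does nothing but the procedures differ by the plan's own d = 0.6 SD, the unpaired two-sided test at 20 per cohort (38 df, noncentrality 0.6 × √(20/2) = 1.90) is significant with probability 0.456. The efficacy rule would then be met by an inert drug.
- If TXA works well and equally, and the procedures do not otherwise differ, the rule is met 5% of the time.
- A difference in efficacy, e_H − e_T, cannot be separated from m_H − m_T: one observed quantity, two unknowns. Covariate adjustment changes the m terms to conditional means and does not identify either e.

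**2. Paired or unpaired.** The plan's figure is more than 15 patients for d = 0.6, power 0.80 and alpha 0.05. With (1.960 + 0.842)² = 7.85:

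- Independent cohorts, two-sided: 2 × 7.85/0.36 = 43.6, so 44 per cohort (45 with the t distribution).
- Paired, two-sided: 7.85/0.36 = 21.8, so 22 pairs (24 with t).
- Paired, one-sided: 18 pairs (19 with t).

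None gives 15, so the sample-size statement does not reveal which test was intended. That discrepancy is a separate issue. For the test itself, no pairing rule exists. Pairs formed by list order would make the p-value depend on that order, leave 20 − 1 = 19 df instead of 38, and discard patients if the cohorts end up unequal. Pairs formed without sight of the outcomes would not by themselves inflate the error rate; the fault is that the analysis is undefined and arbitrary.

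**3. Crude against adjusted, one covariate.** The documents give no imbalance and no correlation, so both are assumed. With within-cohort SDs of 1, a covariate differing by D and correlating r with outcome shifts the crude difference from the adjusted one by r × D. Probability that the crude unpaired test is significant when the adjusted difference is zero:

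| r | D | Shift (SD) | 20 per cohort | 15 per cohort |
|---|---|---|---|---|
| 0.1 | 0.5 | 0.05 | 5.3% | 5.2% |
| 0.1 | 1.0 | 0.10 | 6.1% | 5.8% |
| 0.3 | 0.5 | 0.15 | 7.5% | 6.8% |
| 0.3 | 1.0 | 0.30 | 15.2% | 12.5% |
| 0.5 | 0.5 | 0.25 | 12.0% | 10.1% |
| 0.5 | 1.0 | 0.50 | 33.8% | 26.2% |

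For scale, an assumed within-cohort age SD of 8–12 years makes 0.5–1.0 SD a gap of 4–12 years, within an eligible range of 60 − 18 = 42 years.

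**4. Price of adjustment.** For k independent covariates, each differing by D,

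SE² ≈ (1 − k r²) × [2/n + k(D² + 2/n)/(2n − 3 − k)].

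With k = 3, n = 20, D = 1:

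- r = 0.1: 0.97 × [0.1 + 3.3/34] = 0.191, SE 0.437.
- r = 0.3: 0.73 × [0.1 + 3.3/34] = 0.144, SE 0.379.

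The crude SE is √0.1 = 0.316. Simulated mean SEs are slightly lower, 0.431 and 0.375. Over two simulation runs the increase is about 18–37%. Power for a 0.6 SD difference falls from 46% crude to 27–35%. With D = 0.5 it is 38–48%.

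Root-mean-square error about the adjusted difference, adjusted against crude, 20 per cohort:

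| Setting | D = 0.5 | D = 1 |
|---|---|---|
| r = 0.1, biases in one direction | 0.358 vs 0.352 | 0.439 vs 0.439 |
| r = 0.1, one of three reversed | 0.354 vs 0.319 | 0.440 vs 0.332 |
| r = 0.3, biases in one direction | 0.311 vs 0.551 | 0.381 vs 0.956 |

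**5. Preoperative VAS.** Assume r = 0.3–0.5 with 24-hour VAS. If it differs by 0.5 SD, a model without it stays 0.15–0.25 SD off. If it is balanced, only precision improves. With three other covariates at r = 0.1, the residual variance is 1 − 3 × 0.01 = 0.97, and the SE factor is √(1 − 0.09/0.97) = 0.953 to √(1 − 0.25/0.97) = 0.862, about 5–14% smaller.

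**The case against.** The strongest reply is that the objectives are descriptive. They ask whether HTO and TTO patients differ, and the crude comparison answers that. No objective asks for a contrast standardised for age, sex and BMI. This stands, and it is why adjustment is optional. A reader might infer that leaving it out invalidates the primary analysis, or that the 5–34% is a false-positive rate for the trial. The documents support neither: those rejections are errors only for the adjusted contrast, and for the stated objective they are real cohort differences.

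The size of any confounding is also entirely assumed. At r = 0.1 the rejection rate stays near nominal; 34% needs r = 0.5 and a full 1 SD gap together. Adjustment may even lose. All of this stands.

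On pain, the list of preoperative data is introduced as an inclusion, so it may not be exhaustive, and the Rationale describes chronic knee pain in both groups. One can say only that no preoperative VAS is listed, and that this touches a secondary endpoint.

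Finally, the efficacy wording and the paired test are separate from adjustment and lend it no support. Agreed: they are ranked apart below. None of the objections rescues either of them.

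**Conclusion.** Two statements are wrong as written. The efficacy reading fails by design: with TXA given to all, neither a significant nor a non-significant HTO–TTO difference says whether TXA works, or whether it works better in one procedure. The paired t-test has no pairs to work on. Neither conclusion depends on an assumption about effect size or imbalance.

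The lack of adjustment is not an error. A supportive adjusted estimate could be informative, but its worth cannot be established from the documents: the shift is 0.05–0.50 SD under assumed inputs, and the benefit disappears or reverses when covariates are weak. A reader might infer that adjustment would turn the comparison into evidence on TXA or isolate the effect of the procedure. It does neither, because diagnosis determines procedure and no patient goes without TXA.

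**What to change.** **Needed.**

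1. Replace the efficacy sentence in Data Analysis and the efficacy wording in the Rationale with: *the comparison describes a between-procedure difference among TXA-treated patients and cannot show TXA efficacy, with or without adjustment.*
2. Replace the paired test with an unpaired one (for example Welch's t-test), keep Mann-Whitney as the fallback, and report the crude difference with its 95% CI as the main result.

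Both cost only wording.

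**Optional, prespecified as supportive.**

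3. Beside each crude result, report a linear-model estimate adjusted for age, sex and BMI, for three outcomes: blood loss (transformed if skewed), day-1 VAS and the one-week swelling ratio. State that day 1 means the 24-hour assessment, since the two schedules word it differently. First reconcile the contralateral-limb definition of swelling with the preoperative-value definition. Do not adjust for operative time, which follows from the procedure.
4. Record one preoperative VAS and use it in the pain model only.

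The optional part costs one question before surgery and three degrees of freedom (four for pain). If all covariates differ by 1 SD (r = 0.1–0.3), the SE at 20 per cohort grows by about 18–37% with three covariates and 21–48% with four. The adjusted estimate should therefore not replace the crude one.
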